4.1.2 Patient Follow Up Survey

The follow up surveys will either be mailed to the participant, along with a return envelope, provided electronically and/or by text message via REDCap survey link, or completed via phone or Zoom call with a staff member, according to patient preference. For patients who opt to complete their follow-up surveys via phone or Zoom call, study staff will not assist them in selecting the correct answers for questions pertaining to their understanding of cancer and genetics. Study staff will follow-up with patients once a week within 2–3-week window to encourage completion of the survey. We will attempt to contact non-responders up to five times to encourage survey participation.

Understanding of personal genomic knowledge will be assessed through an adapted version of a measure created by Freedman and colleagues¹, which evaluated women's knowledge of their personal cancer ER and HER2 status using a two-item question (3 response options; yes/no/I don't know). Our adapted questions will evaluate patients' recall of genomic testing results and the implications of their results (i.e., harmful and unknown). Patient recall will be assessed at all survey timepoints (i.e., at baseline, 10 days, 3 months and 9-months following results disclosure with a clinician).

Engagement in care will be assessed by a novel item that queries patients as to whether WES prompted questions to care providers (yes, no, don't know). We will use items adapted for our CSERII study to ask patients if they recall changes to their cancer treatment as a result of their genomic test results. We will also assess engagement via interactive functionality of HOPE-Genomics (see below). Seeking and sharing information about genetic tests will be assessed using two items from the Health Information National Trends Survey (HINTS) 4 that were adapted for our CSERII study.⁷

Satisfaction with physician/patient communication around the results of gene testing will be assessed with a 7-item measure adapted from HINTS 3 & 4. Satisfaction with care will be assessed using a single item measure from Charles and colleagues that was created to evaluate satisfaction with genetic counseling and that was adapted for our CSER1 study.¹⁴ We have also included two novel questions to assess whether patients (1) recalled asking their healthcare providers about their genetic test results and (2) recalled receiving a copy of their genetic test report.

Psychosocial impact of genetic testing and patient uncertainty will be assessed using both the adapted PAGIS Certainty Scale and the FACToR.²³ The FACToR is a 12-item measure developed by CSER1 colleagues at the University of Washington that applies across disease contexts and also includes items related to uncertainty, test-related distress, and positive experiences. Uncertainty about genetic testing results will be assessed using the PAGIS. A 5-item measure by Read and colleagues (Psychological Adaptation to Genetic Information Scale; PAGIS certainty subscale).⁸

Tool usability/usefulness/acceptability will be assessed for patients who view the HOPE-Genomics tool (Arms 2 and 3) approximately 10 days and 3 months after results disclosure. HOPE-Genomics usability/acceptability will be assessed using two instruments. To assess system usability, we will use the System Usability Scale (SUS).⁹ The SUS is a 10-item measure that evaluates a variety of aspects of system usability including the perceived complexity of a system and the need for support and training to facilitate use. We will also use an adapted version of the Electronic Self-Report Assessment-Cancer (ESRA-C).¹³ The ESRA-C is a 6-item measure that assesses participants' opinions about a web-intervention (e.g., easy and enjoyable, acceptability of time required to navigate, overall satisfaction). The ESRA-C is written at a 5th-grade reading level and is highly reliable (Cronbach alpha 0.76).

Motivations for sharing genetic test results will be assessed using a modified 9-item measure adapted from our CSERII study and the Development of the Informing Relatives Inventory (IRI) by de Gues and colleagues.¹⁰ Patients will be asked to rank the importance of various reasons for sharing genetic test results on a 5-point scale, from "Not At All Important" to "Very Important." This measure will only be included in the 3-month follow-up survey and will be included as an exploratory measure.

4.2 HOPE-Genomics Tool Details & Security Features

The HOPE-Genomics tool is a web-based, interactive tool that provides personalized genomics results and educational content to patients. The tool was designed with stakeholder feedback and we have collaborated closely with the COH Research Informatics group to build a fully functioning HOPE-Genomics tool on the HL7 SMART on FHIR platform. For this effort, Research Informatics has built a Web-based responsive application that can be accessed through any popular web browser using devices with varying screen sizes, like computers, tablets, and mobile phones.

Securing the application and the patient data is one of the design principles of this platform; application enforces two-factor authentication for its users to login, when a user signs up for an account, he/she will have to provide a phone number during the registration process. Subsequently the user will have to enter a code sent to the phone (number used during registration) along with the password to login to the application. The application backend uses a JSON Web Token mechanism to authenticate every request coming into the server. A secure token is generated upon user login, and token should be attached to every request to the backend API for the request to be successful. Tokens automatically expire after 30 mins of non-usage and forces the user to login again.

The application also offers secure authorization mechanism, application backend authorizes every data request to make sure the user requesting the information is authorized to view the information. The authentication token when generated is assigned to a patient resource, and data related to that patient resource can only be retrieved from the API using the token generated. The application is also hosted within City of Hope firewall keeping it secure from various vulnerabilities. The application is made available on https to enforce end-to-end secure connection between the patient's browser and the application server. The tool also offers some administrative capabilities, this tool provides direct access to all enrolled patients and allows the study team to manage patient's account details. Each patient user is assigned a FHIR ID that cannot be linked or traced back to the patient's MRN. Lastly, no PHI is captured through the HOPE-Genomics platform, as patients are not asked to input any personal information into the application, and it is not directly linked to the electronic medical record. Our informatics team performs cybersecurity scans every week on the entire HOPE-Genomics application to look for any vulnerabilities. They will then assess the severity of any detected vulnerabilities and fix them as needed.

4.3 Tool Access and Patient Pre-Education Survey

After enrollment, all participants will be provided with a hard-copy or electronic educational pamphlet about whole-exome sequencing (WES). Patients in the Return of Results plus Pre-test Education arm will be provided with login and dual-factor authentication instructions and have immediate access to educational content in the tool, with their sequencing results to become available in the tool shortly after their results are available in Epic. Patients in the Return of Results Only arm will not be able to see tool content until their genomic test results are available (e.g., ~2-6 weeks after sample collection). Patients in the Usual Care arm will have access to the tool content after completing all study surveys, approximately ~9 months after their sequencing results are available.

Approximately 2-3 days after completing the baseline survey, patients in all study arms will complete a pre-test education survey that assesses general genomic knowledge prior to results disclosure. For patients requesting paper versions of the baseline and pre-test surveys, we will mail the pre-test survey 1 week after mailing the baseline. This will ensure that patients who opt for paper surveys can complete the pre-test survey within 2-3 days of completing their baseline survey. As with all study surveys, patients will also have the option of completing the pre-test education survey over a scheduled phone or Zoom call with a study staff member. During the phone or Zoom call, study staff will not assist patients in selecting the correct answers for questions pertaining to their understanding of cancer and genetics. As mentioned above, patients in the Return of Results plus Pre-test Education arm (Arm 3) will view the HOPE-Genomics tool prior to their results disclosure and completion of this survey. The HOPE-Genomics tool will be populated with educational material about genomics, cancer, and other related content, but without the patient's individual test results. We will track Arm 3 patients' tool access through Google Analytics, which is an IT-approved software that monitors user interaction metrics within the HOPE-Genomics platform, specifically button clicks per page, page scrolls, double clicks, and page-viewing duration times. We are utilizing Google Analytics to better understand which features of the tool are most frequently used by patients and identify technical aspects of the tool that need improvement. The version of Google Analytic implemented (GA4) in the HOPE-Genomics platform has a process of data anonymization, so no IP address or other PHI is collected from the participants. In addition, Google Analytics does not gather text data from the HOPE-Genomics platform and therefore has no access to potential PHI within the HOPE-Genomics platform. Additional security features of the HOPE-Genomics platform are discussed in Section 4.2 of this protocol (HOPE-Genomics Tool Details & Security Features). Study staff will call and/or email patients in the Return of Results plus Pre-Test Education arm within approximately 24 hours of receiving their login information to track whether patients interact with the HOPE-Genomics platform and if patients have not accessed the tool, study staff will encourage and facilitate intervention use. All other patients (Usual Care & Return of Results Only) will only view the WES pamphlet before completing this survey. The HOPE-Genomics educational content will be available to those patients in the Return of Results Only and Usual Care arms but will only be made available after their genomic test results are available in the tool.

To improve patient compliance to study requirements, all patients will be presented with the option to opt-in to receive text message reminders related to study participation and to receive access to unique survey links. Patients will have the option to opt in and opt out of receiving text message reminders at any point during their participation; the decision would not affect their participation in the study. For patients who have agreed to provide their mobile number for text message reminders, this method will be used to supplement electronic communication reminders to encourage and facilitate intervention use. Mobile numbers will be collected solely for the purposes of communicating study-related requirements to patients and will not be used to disclose any PHI nor will they be shared for purposes beyond this study and without patient consent. Information detailed in text message correspondences will reference time points and reminders of which patients will need to:

1. Complete a study procedure (e.g., view HOPE-Genomics platform, complete a survey)
2. Be provided with unique survey links generated by REDCap (i.e., links for Baseline, Pre-test Education, 10-day Follow-up, 3 Month Follow-up and 9 Month Follow-up surveys).

Patients who have opted to receive reminders through their mobile phone will receive an initial message acknowledging their opt-in. Frequency of follow-up reminders to complete study procedures will be dictated by patient preference (i.e., patients prefer reminders only by text message), study arm assignment, and/or with regards to timeliness of completion of study requirements. Frequency of text messages will mimic the schedule for automated email reminders:

- **Baseline Survey:** every 96 hours
- **Pre-Test Tool Viewing (Arm 3):** 24 hours after login instructions sent
- **Pre-Test Survey:** every 96 hours
- **HOPE Tool Viewing (Arms 2/3):** 5 days after login instructions sent
- **All follow-up surveys:** Every 2 weeks

There will be a total of five time points of which patients will be provided survey links through text message. These time points correspond to the required completion of surveys as follows: Baseline survey, Pre-test Education survey, 10-day Follow-up survey, 3 Month Follow-up survey and 9 Month Follow-up surveys.

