4.0 STUDY PROCEDURES

4.1. Informed Consent and Baseline Survey

Potentially eligible patients will be approached by study team members for verbal informed consent, either by mail/ email, during clinic visits, or by phone. Patients will receive a study packet that will contain an invitation letter, interest postcard, return envelope, and informed consent document. Patients will be randomized into one of three arms immediately after enrollment. Arm 1 is usual care, Arm 2 is return of results only in the HOPE-Genomics tool, and Arm 3 is return of results plus pretest education in the HOPE-Genomics tool.

Arm 1 patients will receive

a pamphlet (20430 Educational Brochure in iRIS) about WES after they enroll. Their clinician will return their genomics test results in a typical manner, without the assistance of the HOPE-Genomics tool.

Arm 2 patients will receive their genomics test results both from their clinician and from the HOPE-Genomics tool but will only view the tool after their results are available. Arm 3 patients will view the HOPE-Genomics tool (containing educational content) before their sequencing results are available. These patients will also receive their genomics test results both from their clinician and from the HOPE-Genomics tool. After completing all study surveys at 9 months post results disclosure, participants in Arm 1 (usual care), will receive access to the HOPE-Genomics tool, which will contain both the educational information and the personalized genomics results.

Table 1: Outcome and covariate data collection

			Patient surveys			MRA
	Baseline	Pre-edu. survey	T1	T2	T3	
Genetic Care outcomes						
MD recommendations						
Screening, surgery, meds			X	X	X	X
Referrals GC, specialists			X	X	X	X
Cascade testing			X	X	X	X
Patient utilization/behavior						
Screening, surgery, meds			X	X	X	X
Consult GC, specialists			X	X	X	X
Inform family members			X	X	X	
Cascade testing			X	X	X	
Patient-centered outcomes						
Recall of results	X		X	X	X	X
Understanding of results			X	X	X	
Genomic knowledge	X	X	X	X		
Engagement in care			X	X	X	
Information seeking				X		
Psychosocial impact	X		X	X	X	
Follow up outcomes						
HOPE-Genomics usability			X	X		
Satisfaction with MD-patient communication and care			X	X		
Covariates						
Socio-demographics	X					X
Clinical information						X
Other (e.g., health literacy)	X					X

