4.4 Results Disclosure

We expect results to be available within ~3-14 days of sample acquisition. We will monitor the patients' laboratory data to see when results have been finalized. Lab results and variant interpretations for the HOPE Genomics intervention will be stored in a custom genomic database designed by COH Research Informatics. All results will be validated by study staff before data are input into the HOPE-Genomics tool. All clinicians will receive results through the EHR. Additionally, clinicians with patients in the intervention arm will also be able to view their patients' results through the HOPE-Genomics after individual-level patient data have been entered into HOPE-Genomics. Results will be available to patients in the HOPE-Genomics app approximately 3-14 days after they are available in the EHR.

At this time, we will ask patients in the Return of Results Only intervention arm, (Arm 2) and the Return of Results + Pre-Test Education arm (Arm 3) to log into the HOPE-Genomics tool on their own time. Study staff will provide patients with instructions to create an account and log into the tool using dual-factor authentication. Study staff will track patients' tool access through Google Analytics and call or send automated RedCap reminders to encourage tool use, if necessary. Study staff will track patients' tool access through Google Analytics and call and/or send automated REDCap reminders to encourage tool use, if necessary. In addition, the study staff will be available to help patients access HOPE-Genomics at subsequent clinic/infusion visits or via secure web conference at any point in time following the disclosure of their test results until the end of the study (with coordination with the study team).

Patients in the control arm (Arm 1) will have their results returned in clinic by their provider, with no changes to the clinician's typical delivery method. Patients will be provided an educational pamphlet that generally describes sequencing and will granted access to the HOPE-Genomics tool with their results after completing all follow-up study surveys, approximately 9 months after their results are in the EHR.

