4.5 Follow up Surveys

4.5.1 10-Day Follow-Up Survey

All patients enrolled in the study will be asked to complete a follow-up survey approximately 10 days after results are released in the EHR. The survey will either be mailed to the participant, provided electronically and/or by text message via REDCap survey link or completed over a scheduled phone or Zoom call with a staff member, according to patient preference. If the survey is mailed, the patient will be provided with a return envelope. Follow-up survey reminders will be similar to those outlined for the baseline survey. The follow-up survey outcomes are detailed in Table 1. For participants of both intervention arms, the survey will also include questions about the usability of HOPE-Genomics. Survey measures will be similar to measures detailed in Section 4.1.1.

Patients in Arm 1 (usual care) will receive a modified survey that does not contain questions that pertain specifically to the HOPE-Genomics tool, like usability.

4.5.2 3 Month Follow-Up Survey

Delivery of the follow-up survey and study materials will follow similar procedures mentioned in Section 4.3.1. The 3 Month follow-up survey outcomes are detailed in Table 1. Survey measures will be similar to measures detailed in Section 4.1.1.

4.5.3 9 Month Follow-Up Survey

Delivery of the follow-up survey and study materials will follow similar procedures mentioned in Section 4.4.1. The 9 Month follow-up survey outcomes are detailed in Table 1. Survey measures will be similar to measures detailed in Section 4.1.1. Participants in the Usual Care Arm will view their results in the HOPE-Genomics tool after completing the 39Month Follow-Up Survey. None of their follow-up surveys will contain questions pertaining to the HOPE-Genomics tool or its usability.

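### The tool-access rule for Usual Care is stated inconsistently: Section 4.3 and the physician letter can be read as opening the tool to controls before the outcome surveys, and the 9-month release overlaps the 12-month Aim 2 window

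*Combined protocol and SAP*

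**What the plan says.** Three places give the same rule for Arm 1:

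- Section 4.1: "After completing all study surveys at 9 months post results disclosure, participants in Arm 1 (usual care), will receive access to the HOPE-Genomics tool".
- Section 4.3, opening paragraph: "Patients in the Usual Care arm will have access to the tool content after completing all study surveys, approximately ~9 months after" results are available.
- Section 4.4: Arm 1 receives "access to the HOPE-Genomics tool with their results after completing all follow-up study surveys, approximately 9 months after their results are in the EHR".

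Two places differ:

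- Section 4.3, at the end of the paragraph on the pre-test education survey, treats Arm 2 and Arm 1 together. It describes educational content as "available to those patients in the Return of Results Only and Usual Care arms but will only be made available after their genomic test results" have been loaded in the tool. The sentence mentions neither surveys nor 9 months.
- Appendix A, the letter to the treating physician, says that a patient who enrols will have the tool with their own results about 3 days after those results appear in EPIC. It makes no exception for the control arm.

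Section 4.5.3 has a garbled time point: "Participants in the Usual Care Arm will view their results in the HOPE-Genomics tool after completing the 39Month Follow-Up Survey".

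On timing, Section 4.4 says results reach the app about 3 to 14 days after the EHR and does not limit that statement to any arm. Section 4.5.1 places the primary survey about 10 days after EHR release. Section 6.2.2 counts Aim 2 care over 12 months from disclosure.

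**The concern.** The primary contrast in Section 6.2.1 is usual care against any exposure to the tool, so it depends on Arm 1 not having the tool when recall is measured. Staff who worked from the shared sentence in Section 4.3 would open content to Arm 1 on the Arm 2 schedule, and a clinician who read the letter would expect a control patient to have access within days. If the tool works, exposed controls recall more and the estimated difference shrinks. The trial could then report little or no benefit for a reason unrelated to the tool.

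Such exposure could also go unnoticed. Arm 1 surveys carry no tool questions, the access tracking in Sections 4.3 and 4.4 is described for the intervention arms, and the plan describes no check for tool use among controls.

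The stated rule has a problem of its own: release at about 9 months comes before the Aim 2 window closes.

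**Working it through.** **1. Timing under each wording, in days after results reach the EHR**

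| Source | Arm 1 access opens | Relative to the 10-day survey | Relative to the 3- and 9-month surveys |
|---|---|---|---|
| Sections 4.1, 4.3 (opening), 4.4 | after all surveys, about 9 months | after | after |
| Section 4.3 shared trigger, with the Section 4.4 loading time | day 3 to 14 | before or after | before both |
| Appendix A | about day 3 | about 7 days before (10 − 3) | before both |

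Under the shared trigger, access precedes a day-10 survey only where results load early in the 3-to-14-day range. Late answers widen the overlap: the Usual Care letter (Appendix L) gives about 2 weeks for this survey, and Section 4.1.2 allows weekly follow-up over 2 to 3 weeks.

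**2. The plan's own power figure**

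Inputs from Section 6.2.1: p1 = 0.39, p2 = 0.39 + 0.15 = 0.54, n1 = 130, n2 = 260, two-sided alpha 0.05.

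Power = Φ{ [ (p2 − p1) − 1.96·√( p̄(1 − p̄)(1/n1 + 1/n2) ) ] / √( p1(1 − p1)/n1 + p2(1 − p2)/n2 ) }

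- p̄ = (0.39 + 2 × 0.54)/3 = 0.49
- 1.96·√(0.49 × 0.51 × (1/130 + 1/260)) = 0.1052
- denominator √(0.2379/130 + 0.2484/260) = 0.0528
- (0.15 − 0.1052)/0.0528 ≈ 0.848, so power is 80.2%. The stated 80% reproduces.

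**3. Illustration of dilution**

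Assume a share c of Arm 1 sees the tool before answering and gains the full 15 points, so p1 = 0.39 + 0.15c. The documents give no value for c.

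| c (assumed) | p1 | difference | power |
|---|---|---|---|
| 0 | 0.390 | 0.150 | 80.2% |
| 5% | 0.3975 | 0.1425 | 75.9% |
| 10% | 0.405 | 0.135 | 71.3% |
| 20% | 0.420 | 0.120 | 60.9% |

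The gain is assumed too. If 10% were exposed but gained only half (7.5 points), p1 would be 0.39 + 0.10 × 0.075 = 0.3975, which is the 75.9% row.

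**4. Aim 2 window**

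12 months − about 9 months = about 3 months, a quarter of the window, during which Arm 1 may have the tool even if the stated rule is followed exactly.

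**The case against.** The case against a serious problem is strong. The 9-month rule is stated plainly three times, once at the start of the same Section 4.3. The shared sentence can be read as setting an earliest point rather than a release date: content is "Usual Care arms but will only be made available after their genomic test results are available in the tool". If Arm 1 results are loaded only at 9 months, that agrees with the other sections. The sentence before it is about keeping Arms 1 and 2 to the pamphlet before the pre-test survey. Access needs an account and two-factor login, only Arms 2 and 3 are asked to log in (Section 4.4), and the tool-viewing reminders and the invitations in Appendices G and H are for intervention arms.

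Most of this stands, and it makes early exposure a risk of misreading, not the plan. It does not remove the inconsistency. No passage says that loading of Arm 1 results is held back, the loading statement in Section 4.4 names no arm, and Appendix A has no such alternative reading.

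A reader might also infer from Section 4.5.3 that controls get the tool at 3 months. The documents do not support that. The garbled time point sits under the heading for the 9-month survey, in a paragraph about that survey, and the other sections agree on 9 months. It is a typing error.

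**Conclusion.** The wording conflict is real and should be corrected, because it bears on what the control arm receives. The 9-month rule is the evident intent. If the shared sentence in Section 4.3 or the physician letter were followed, controls could see tool content around the primary survey and would have access before the 3- and 9-month surveys. If the tool works, the bias would be toward no difference.

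The size is unknown. The fall from 80% to 71% assumes that 10% of controls are exposed before answering and that each gains the full 15 points. The gain is likely to be smaller, since the Section 4.3 sentence concerns educational content while the primary outcome is recall of the patient's own somatic results. A reader might infer that controls will be exposed, or that the trial's real power is 71%; the documents support neither.

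The Aim 2 overlap of about 3 months depends on no misreading. It follows from the stated release time and the stated outcome window.

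**What to change.** 1. In the closing sentence of the pre-test survey paragraph in Section 4.3, remove the reference to the Usual Care arm, or add that for Usual Care the content opens only once all study surveys are completed.
2. In Appendix A, limit the sentence on access about 3 days after results to patients assigned to an intervention arm.
3. In Section 4.5.3, correct the time point to 9 months.
4. Set Arm 1 account release in the tool's administration to match the rule in Sections 4.1, 4.3 (opening paragraph) and 4.4.
5. Reconcile the 9-month release with the 12-month window in Section 6.2.2. Either delay Arm 1 access to the end of the window, or end the Aim 2 count at 9 months in all arms, or keep both and state how Arm 1 care after release will be handled.

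Items 1 to 4 cost three wording corrections and one account setting, with no new procedures. Item 5 has a modest cost: about 3 more months' wait for control patients under the first option, or loss of care events in months 9 to 12 under the second.
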